**Liposomal Bupivacaine in Adductor Canal Blocks Before Total
Knee Arthroplasty Leads to Improved Post-Operative
Outcomes: A Randomized Controlled Trial**

NCT: NCT04910165

Date: 4/01/2020

Purpose: To explore the effectiveness of Exparel (liposomal bupivacaine) in Adductor Canal Blocks for peri-operative pain control following a total knee arthroplasty (TKA) procedure: reduce opioid requirement use postoperatively, reduce pain scores postoperatively, provide earlier mobilization, and decrease length of hospital stay.

Methods: Our double blinded (patient and orthopaedic department) prospective randomized controlled study will collect 100 patients who receive an adductor canal block with Exparel and compare it with 100 patients who received an adductor block with ropivacaine. Each patient will be randomized using an online number generator. Only the anesthesiologist will be privy to which medicine was used in the block, with both the patient and the surgeon being blinded. Patients will either receive Exparel 20 ccs with 5 ccs of 0.5% bupivacaine in the adductor canal block and 20 ccs of 0.2% Ropivacaine in the iPACK block (Exparel group) or 25 ccs of 0.2% ropivacaine in the adductor canal block, and 20 ccs of 0.2% ropivacaine in the iPACK block (control group). These blocks will be placed in the pre-operative holding area under ultrasound guidance. Intraoperatively, patients will receive a spinal anesthetic utilizing 0.75% hyperbaric bupivacaine at the L3-4 or L4-5 levels and a propofol infusion for IV sedation. Patients will be seen in the PACU area, where pain scores and oral morphine equivalents (OME) are calculated. Patient will be seen on POD 1 to discuss expectations of pain control and goals for pain management (i.e. use of multimodal pain regimen and goals to decrease opioid use). Pain scores and OMEs will be calculated for POD 0-3. Progress notes in EPIC and patient interview will also disclose if patient had PT/mobilization early. We will finally review EPIC encounter for length of admission (date of admission to date of discharge), complication rates from the block, and readmission for pain.

Inclusion Criteria: Undergoing unilateral primary TKA for a diagnosis of knee osteoarthritis without additional concomitant procedures

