Exclusion Criteria: Not undergoing a TKA after initially signing up for surgery, if they do not undergo spinal analgesia (due to medical contraindications or a failed attempt by the anesthesiologist), if the proper suspension or local anesthetic mixture is not utilized for the block due to physician error, or if they voluntarily drop out during the study period.

Risks and Benefits of Exparel:

Risks-side effects of Exparel include N/V, HA, and dizziness. As with any local anesthetic, more serious risks may include local anesthetic toxicity (neurologic and cardiac symptoms, cardiac arrest)

Benefits-Improved peri-operative pain control: we aim for a modest reduction of opioid use during the postop period (<60 oral morphine equivalents during first 2-3 days), decrease length of hospital stay (by 0.5-1 day), and reduction in pain scores

Study Visits:

Pre-op - Patient seen in Ortho office for initial consent to TKA and to fill out questionnaire (see attached). **Day of Surgery**- patient consented in the preoperative holding area with anesthesia, where blinding process occurs. Adductor canal block placed preoperatively.

After surgery- We will visit the patient in PACU to ask about pain scores and determine amount of opioid IV used in PACU. We will also visit the patient in POD 1 to discuss expectations of pain control. We will also look in EPIC to determine pain scores and OMEs during POD 0, 1, 2, and 3

Post-op visits 1,2, 3, and 4- Pain scores, WOMAC questionnaire scores, and opioid usage amounts collected

Sample Size Calculation:

1. LOS: 2.97 days (controls)-To detect a difference of .5 days (from 2.47 to 2.97, assuming the Exparel group has lower LOS), you need at least 41 patients per group if you assume a homogeneous population and 64 patients per group if you expect there to be greater heterogeneity.
2. NRS Pain score: 6 (controls)-To detect a difference of 1.41 points (from 4.59 to 6.00, assuming the Exparel group has lower pain), you need at least 22 patients per group if you assume a homogeneous population and 53 patients per group if you expect there to be greater heterogeneity
3. WOMAC: 21.5 point difference between pre op and post op score (expect a bigger difference in Exparel group)-To detect a difference of 15 points (21.5 for controls, 36.5 for Exparel patients), you need at least 11 patients per group if you assume a homogeneous population and 17 patients per group if you expect there to be greater heterogeneity.

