Outcomes: WOMAC outcome scores (taken pre-operatively, and at 1 week post-operative visit, 2 week post-operative visit, 4 week post-operative visit, and 6 week post-operative visits), NRS Scores (taken on every hospital day and post-operative visit), Opioid Use (inpatient and outpatient), Hospital LOS, and hospital outcomes (complication, inpatient rehab, and readmission rates)

Analysis: Categorical and ordinal variables will be compared using Chi Squared and Fischer's Exact tests as appropriate, while numerical variables will be analyzed using Mann-Whitney-U tests. (IBM SPSS Version 23 Statistics for Windows, Armonk, NY: IBM Corp). For all analyses, $p < 0.05$ denotes statistical significance.

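### Opioid use is listed by setting with no time window, so a shorter stay alone could lower inpatient and raise outpatient opioid if those totals are compared between arms

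*Combined protocol and SAP*

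**What the plan says.** All references are to the combined protocol and SAP.

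- **Outcomes** lists "Opioid Use (inpatient and outpatient), Hospital LOS". The opioid item has no time window, per-day rate or combined total.
- **Analysis** sends all numerical variables to Mann-Whitney U tests at p < 0.05. It does not name the opioid summary to be tested.
- **Sample Size Calculation, item 1** plans on a shorter stay with Exparel: "To detect a difference of .5 days (from 2.47 to 2.97, assuming the Exparel group has lower LOS". The Benefits text hopes to "decrease length of hospital stay (by 0.5-1 day").
- **Methods** uses calendar days: "Pain scores and OMEs will be calculated for POD 0-3". **Study Visits** repeats this and names the source: "We will also look in EPIC to determine pain scores and OMEs during POD 0, 1, 2, and 3".
- **Study Visits** also covers the period after discharge. At post-operative visits 1 to 4 the entry is "Pain scores, WOMAC questionnaire scores, and opioid usage amounts collected".
- The **Benefits** text states the opioid aim over early days: "<60 oral morphine equivalents during first 2-3 days".

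**The concern.** Discharge happens after randomisation, and its timing is itself a trial outcome that the plan expects to differ between arms. An opioid total that stops at discharge therefore mixes two things: how much opioid a patient takes per day, and how many days the patient stays. If daily use is the same in both arms and one arm goes home sooner, that arm has less inpatient and more outpatient opioid. Complete recording of every dose would not remove this, because the cause is where the total is cut.

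Lower opioid requirement is the first aim named under Purpose. A significant reduction in inpatient opioid could be the length-of-stay (LOS) result counted a second time, and the outpatient comparison would be distorted against Exparel.

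**Working it through.** **1. Inputs from the document.** LOS means of 2.97 (control) and 2.47 days (Exparel); 100 patients per arm; Mann-Whitney U; p < 0.05. The document gives no OME mean, SD or time course, and no SD for LOS.

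**2. The plan's own LOS figure.** For LOS it says "you need at least 41 patients per group if you assume a homogeneous population and 64 patients per group" with greater heterogeneity. SD, power and sidedness are not stated, so this cannot be strictly reproduced, but an SD can be backed out. From n = 2(z₁ + z₂)²SD²/δ², SD = δ√(n/2)/(z₁ + z₂). Taking two-sided 5% and 80% power, z₁ + z₂ = 1.960 + 0.842 = 2.802:

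- n = 41: 0.5 × √20.5 / 2.802 = 0.81 day
- n = 64: 0.5 × √32 / 2.802 = 1.01 days

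These give a reasonable LOS SD for the simulations.

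**3. Shift with equal daily use.** The half-day difference is 0.5/2.97 = 16.8% of the control stay. As an illustration, assume 20 OME per day in both arms for 14 days (280 in total):

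| | Control | Exparel | Difference |
|---|---|---|---|
| Inpatient | 20 × 2.97 = 59.4 | 20 × 2.47 = 49.4 | −10 (−16.8%) |
| Outpatient | 280 − 59.4 = 220.6 | 280 − 49.4 = 230.6 | +10 (+4.5%) |
| Total | 280 | 280 | 0 |

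If use declines over time, the late hospital days carry less opioid and the inpatient shift is smaller in percentage terms.

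**4. How often the test would be significant.** Simulations used 100 per arm, no difference in daily use, opioid use independent of stay, and between-patient CV 0.5 to 1.0. LOS SD was 0.81 or about 1.0.

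*Set-up A:* whole-day stays, day-to-day variation within patients, and use either flat to POD 3 or decaying with a 2- or 4-day time constant.

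- Mean inpatient OME is about 9 to 16% lower on Exparel.
- The inpatient comparison is significant in roughly 9 to 50% of trials.
- A fixed-window total counted in both settings is significant in 4 to 7%.

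*Set-up B:* continuous gamma-distributed stays, no day-to-day variation, and use over 14 days either flat at 20 OME per day or falling from 30 to 5.

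- The inpatient comparison is significant in about 24 to 69%.
- The 14-day total is significant in 4.5 to 5.6%.
- With no LOS difference, the inpatient comparison is significant in 4.5%.

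Across the set-ups tried, the outpatient comparison is significant in anything from 6 to 83% of trials, with the distortion running against Exparel.

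**5. Does the POD 0-3 window help?** With gamma stays, 85 to 89% of controls and 92 to 96% of Exparel patients leave before day 4. If the EPIC values hold only in-hospital doses, the POD 0-3 total is still cut at discharge for most patients. It is then significant in 9 to 50% (set-up A) or 22 to 67% (set-up B). If home doses are included it returns to about 5%. Comparing days separately (POD 0, POD 1, or POD 2 among those still in hospital) gave 4.4 to 6.4% under set-up A's assumptions with LOS SD 1.0.

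**The case against.** The strongest reply is that the plan never specifies a total cut at discharge. The parenthesis in Outcomes may only mean that both settings are covered. Methods and Study Visits both measure by calendar day, and the stated aim concerns the first 2-3 days. The neighbouring pain-score item is also collected by hospital day and visit. On that view Outcomes is a list of headings: inpatient use means the POD 0-3 values, and outpatient use means the amounts at visits 1 to 4.

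Much of this stands. A reader might infer that the plan defines a discharge-split total and commits to testing it, or that Methods and Outcomes contradict each other. The text supports neither: the split is the ordinary meaning of the words but is not written, and the sections can be read together. Day-by-day comparison would also avoid the artefact in the model used here, although for POD 2-3 that relies on opioid use being unrelated to who is still in hospital.

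The reply does not close the matter. Nothing says which opioid measure is tested, and the POD 0-3 values come from EPIC while the expected mean stay is 2.5 to 3 days. Home doses on POD 2-3 are not addressed.

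Two further points are fair. The artefact needs a real LOS difference, though that is what the trial plans for. And reporting both components would reveal the opposite shifts, so the practical risk is that the inpatient result is interpreted alone.

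**Conclusion.** The concern holds conditionally. If inpatient and outpatient totals are compared, a half-day shorter stay lowers the first and raises the second with no opioid effect. The inpatient reduction is up to about 17% at constant use. The direction follows from the definition when daily use is equal.

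The error rate is much less certain. Roughly 9 to 50% instead of 5% is a fair working range, and one less variable model reached 69%. It rests on assumed CVs, LOS SDs and time profiles, on a full 0.5-day LOS effect, and on opioid use being independent of stay. It should not be read as the trial's actual false-positive rate. Nor should a reader infer that any opioid reduction found would be spurious: a fixed-window total that includes home doses is free of the artefact.

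The POD 0-3 text protects against the problem only if home doses are counted or each day is compared separately, and the plan states neither. Opioid use is not one of the three sample-size endpoints, but it is the first-named aim, so the outcome should be defined before analysis.

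**What to change.** - Define the tested opioid outcome as cumulative OME from block placement to fixed times, counting hospital and home doses for every patient.
- Totals to the 1-, 2-, 4- and 6-week visits can be built from amounts the plan already collects, so these need only a change of wording.
- A POD 0-3 total also needs dated home doses for patients discharged before the end of POD 3. No such collection is described, so the 1-week visit should record home doses by day through POD 3.
- State which of these totals is the main opioid measure.
- Report inpatient and outpatient amounts descriptively, labelled as dependent on length of stay and not as evidence of opioid sparing.

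The cost is a revised outcome definition and one added item on the 1-week form. The drawback is that early home doses will rely on patient recall.

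### WOMAC is sized in points of pre-to-post change, but its only stated analysis (read as numerical) is an unadjusted Mann-Whitney test, with no estimate in points and no covariate adjustment for the pre-operative score

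*Combined protocol and SAP*

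**What the plan says.** The Outcomes section lists "WOMAC outcome scores (taken pre-operatively, and at 1 week post-operative visit", with further visits at 2, 4 and 6 weeks, so every patient should have a pre-operative score.

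Item 3 of the Sample Size Calculation works on the change score: "WOMAC: 21.5 point difference between pre op and post op score (expect a bigger difference in Exparel group". It continues: "To detect a difference of 15 points (21.5 for controls, 36.5 for Exparel patients), you need at least 11 patients per group" under a homogeneous population, or "17 patients per group if you expect there to be greater heterogeneity". The planned enrolment is 100 per arm.

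The Analysis section has three elements. "Categorical and ordinal variables will be compared using Chi Squared" or Fisher's exact tests; "numerical variables will be analyzed using Mann-Whitney-U tests"; and p < 0.05 "denotes statistical significance". It does not say which class WOMAC belongs to, or whether the change or the score at each visit is tested. It names no effect estimate, confidence interval, covariate or model.

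**The concern.** The target is set in points, but the only stated criterion for success is a p-value from a rank test. Sizing in points implies that WOMAC is numerical, so Mann-Whitney applies, most naturally to the change score. If WOMAC were read as ordinal, Chi-squared or Fisher's test would give no estimate in points either.

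Two things are at stake. First, enrolment is far larger than WOMAC needs, so a significant result would be compatible with an effect well below the one planned for. Second, subtracting the baseline uses it less efficiently than including it as a covariate, so any interval reported would usually be wider than the data allow.

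WOMAC is not in the Purpose statement, but it is a named outcome and one of the three used for sizing.

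**Working it through.** **Inputs from the plan.** Difference 15 points (36.5 − 21.5); 11 or 17 per group; 100 per arm enrolled; alpha 0.05.

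**Inputs not given, so assumed.** SD of change, power and sidedness; baseline-to-follow-up correlation ρ, taken as 0.3 to 0.7; equal baseline and follow-up variances unless stated.

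**1. The plan's own figures.** 11 and 17 cannot be reproduced directly because SD, power and sidedness are missing. I solved for the change SD at which each is the smallest adequate n, using a two-sample t-test (noncentrality 15 / (SD × √(2/n))), two-sided 0.05 and 80% power:
- n = 11: SD 11.3 to 11.9
- n = 17: SD 14.7 to 15.1

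Across 80% to 90% power and one- or two-sided 0.05, the ranges are 9.8 to 13.7 and 12.7 to 17.2. The stated sizes are plausible.

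**2. Power at 100 per arm.** For 15 points it is 0.9999998 at SD 15 and 0.99998 at SD 17.2. Power is not the problem.

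**3. What p < 0.05 means at this size.** The smallest observed difference reaching significance (t-based) equals the 95% CI half-width:

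t(0.975, 198) × SD × √(2/100) = 0.2789 × SD

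At SD 15 this is 0.2789 × 15 = 4.18 points, and 4.18 / 15 = 28% of the planned effect. Over SDs of 9.8 to 17.2 it is 2.7 to 4.8 points, or 18% to 32%. For the rank test itself, the simulated Hodges-Lehmann half-width at SD 15 with normal scores is 4.29, almost the same.

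**4. Gain from the covariate, against change scores.** Relative variances are 2(1 − ρ) for change and 1 − ρ² for ANCOVA, so the ratio is (1 + ρ)/2.

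| ρ | Variance ratio | CI width ratio |
|---|---|---|
| 0.3 | 0.65 | 0.806 |
| 0.5 | 0.75 | 0.866 |
| 0.7 | 0.85 | 0.922 |

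The half-width at 100 per arm then falls:
- SD 14.7 to 15.1 (from n = 17): from 4.1–4.2 to 3.3–3.9 points
- SD 11.3 to 11.9 (from n = 11): from 3.2–3.3 to 2.5–3.1 points

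If follow-up SD is k times baseline SD, the variance ratio is k²(1 − ρ²)/(1 + k² − 2ρk). The CI width ratio is 0.709 to 0.792 at k = 0.8 and 0.886 to 0.990 at k = 1.25, so the interval is 29% to 1% narrower.

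**5. Gain against the planned rank test.** Simulation: 4,000 trials per case, 100 per arm, no treatment effect, change SD scaled to 15. Half-widths are given for ρ = 0.3 / 0.5 / 0.7.

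| Score distribution | Hodges-Lehmann on change | ANCOVA | Ratio |
|---|---|---|---|
| Normal | 4.29 / 4.29 / 4.29 | 3.38 / 3.62 / 3.86 | 0.788 / 0.845 / 0.901 |
| Moderate skew (0.7) | 4.17 / 4.15 / 4.14 | 3.37 / 3.62 / 3.85 | 0.808 / 0.872 / 0.932 |
| Strong skew (1.4) | 3.80 / 3.74 / 3.69 | 3.34 / 3.59 / 3.82 | 0.879 / 0.959 / 1.036 |

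**6. If visit scores alone were tested.** This reading has less support, since sizing is on change. The ANCOVA variance ratio is 1 − ρ², that is 0.91, 0.75 and 0.51, so variance is 9% to 49% lower.

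**The case against.** The strongest reply is that nothing here is wrong. Mann-Whitney is valid under randomisation, power is near certainty for the planned effect, and a change score already brings in the baseline by subtraction. A Hodges-Lehmann interval on change, with a half-width of about 4.3 points at SD 15, would already separate an effect of 5 points from one of 15, so the interpretability gap can be closed without ANCOVA. The covariate then saves only 0.4 to 0.9 points of half-width (4.29 against 3.86 and 3.38), under assumed correlations and a back-solved SD. With strong skew and ρ = 0.7 it is 4% worse. The same silence about estimates also covers pain scores, opioid use and length of stay.

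Most of this stands, and it limits the size of the point. It does not remove it. The plan commits to no estimate for an outcome it sized in points, and it does not say that change is what will be tested. In eight of the nine simulated cases ANCOVA gave the narrower interval, using data already collected. That other outcomes share the reporting gap is no reason to leave it for WOMAC, where the plan's own 15-point target makes it plainest.

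**Conclusion.** The concern holds. It affects interpretability and precision, not validity, bias or power. As written, the analysis cannot show whether the WOMAC effect is near 15 points or under a third of that, because about 4.2 points suffices for p < 0.05 at SD 15.

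Covariate adjustment is a modest further gain: an interval 19% to 8% narrower than unadjusted change scores for ρ of 0.3 to 0.7. Against the planned rank test it ranges from 21% narrower (normal scores) to 4% wider (strong skew).

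These sizes rest on the assumed correlations, an SD back-solved at two-sided 0.05 and 80% power, and the reading of WOMAC as numerical and analysed as change. The change is one the sponsor should make, but the trial's validity does not depend on it. Confidence is medium.

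**What to change.** State that WOMAC is analysed as a numerical variable. Analyse it by ANCOVA with the pre-operative score as covariate, at one visit chosen by the sponsor and named before unblinding, and report the adjusted mean difference with its 95% CI. Keep Mann-Whitney on change as a sensitivity analysis, with a Hodges-Lehmann shift and CI.

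A mixed model over the four visits is optional. The Exclusion Criteria remove patients "if they voluntarily drop out during the study period", so it would help mainly with intermittently missed visits.

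If Mann-Whitney remains the main analysis, the minimum change is to add the Hodges-Lehmann shift with its CI. That gives an estimate in points but no covariate adjustment.

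The cost is a few sentences and a little more analysis work. No new data are needed, and SPSS, already named, fits ANCOVA. The main result would rest on a comparison of means, which is reasonable at 100 per arm; the possible loss under strong skew is the reason to keep the rank test alongside.

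### No primary endpoint or primary time point is named, and 0.05 applies to every analysis: with no true effect, one test of each of the three sized outcomes gives a significant result 10–14% of the time (assumed correlation 0.8 to 0).

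*Combined protocol and SAP*

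**What the plan says.** The Analysis section assigns tests by type of variable (chi-squared or Fisher's exact; Mann-Whitney) and then says: "For all analyses, $p < 0.05$ denotes statistical significance". It states no sidedness, hierarchy or adjustment.

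The rest of the document does not supply a ranking:

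- **Title.** It announces a result, "Knee Arthroplasty Leads to Improved Post-Operative" outcomes, without saying which outcomes.
- **Purpose.** The trial is described as exploring effectiveness, with four joint aims: "reduce opioid requirement use postoperatively, reduce pain scores postoperatively, provide earlier mobilization, and decrease length of hospital stay".
- **Inclusion Criteria.** The word primary occurs only here, for the type of operation: "Undergoing unilateral primary TKA for a diagnosis of knee osteoarthritis".
- **Sample Size Calculation.** Three outcomes are sized separately. Item 1 is length of stay: "To detect a difference of .5 days (from 2.47 to 2.97, assuming the Exparel group has lower LOS"). Item 2 is NRS pain: "To detect a difference of 1.41 points (from 4.59 to 6.00, assuming the Exparel group has lower pain"). Item 3 is a 15-point difference in WOMAC change (21.5 against 36.5). Items 2 and 3 name no day or visit.
- **Methods and Outcomes.** "Pain scores and OMEs will be calculated for POD 0-3", and NRS is taken again at the follow-up visits. WOMAC is repeated at 1, 2, 4 and 6 weeks. Opioid use, length of stay and hospital outcomes are listed alongside, all at the same level.
- **Risks and Benefits of Exparel.** Opioid use, the first aim under Purpose, is not sized. Its target has a loose window: "<60 oral morphine equivalents during first 2-3 days".

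**The concern.** A trial that sizes three outcomes to detect stated differences, and then calls any p-value below 0.05 significant, has several routes to a positive result and no rule for which one counts. For NRS and WOMAC the choice of day or visit multiplies those routes.

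Two things are at stake. The chance of at least one false-positive finding exceeds the 5% that the significance rule suggests. And nothing in the document stops the headline outcome and time point from being picked once the results are known, which no later analysis can repair. The exploratory wording under Purpose does not fit with sizing to detect differences and a blanket significance rule, so a reader cannot tell whether any test is meant to be confirmatory.

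**Working it through.** **Inputs from the document.** Significance level 0.05 for every analysis (Analysis). Three sized outcomes with per-group sizes, for a homogeneous / more heterogeneous population, of 41/64 (length of stay), 22/53 (NRS) and 11/17 (WOMAC) (Sample Size Calculation). 100 patients per arm (Methods).

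**Not in the document, so assumed.** Correlation between outcomes (range shown), sidedness, power, standard deviations, number evaluable, and the efficiency of the Mann-Whitney test relative to the t-test (0.955, its value for normal data).

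**Step 1: the plan's own sample sizes.** They cannot be reproduced independently because SD, alpha, sidedness and power are not stated. Solving backwards with a two-sample t-test, two-sided 0.05 and 80% power gives SDs of about 0.8/1.0 days, 1.63/2.57 NRS points and 12/15 WOMAC points. For example, with SD 1.0 the normal formula gives n = 2(1.960 + 0.842)² × (1.0/0.5)² = 62.8, so 63, and the t-test version gives 64, as stated. This shows only that the figures are consistent with those settings; one-sided sizing with larger SDs fits as well (1.13 days for the 64). The false-positive figures below do not depend on it.

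**Step 2: three outcomes, one test each, no true effect.** If independent, 1 − 0.95³ = 0.143. The upper bound at any correlation is 3 × 0.05 = 0.15. For z-statistics with common correlation ρ, the chance of at least one rejection is

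1 − ∫ φ(u) [Φ((c − √ρ·u)/√(1−ρ)) − Φ((−c − √ρ·u)/√(1−ρ))]^k du, with c = 1.960 and k = 3.

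**Step 3: a test at each scheduled time point.** Count: NRS on POD 0–3 plus four visits = 8; WOMAC at four visits = 4; length of stay = 1; so k = 13. If independent, 1 − 0.95¹³ = 0.487.

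| Common correlation | 3 tests, two-sided 0.05 | 13 tests, two-sided 0.05 | 3 tests, one-sided 0.05 | 13 tests, one-sided 0.05 |
|---|---|---|---|---|
| 0 | 14.3% | 48.7% | 14.3% | 48.7% |
| 0.3 | 13.6% | 41.8% | 13.0% | 35.8% |
| 0.5 | 12.5% | 33.4% | 11.8% | 28.1% |
| 0.8 | 9.8% | 19.2% | 9.3% | 16.7% |

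Opioid use, mobilization and the hospital outcomes are not counted; testing them too would raise these figures.

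**Step 4: does one primary endpoint fit the planned size?** Take length of stay at its larger stated size, 64 per group, and assume 80% power.

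- If 64 came from a two-sided 0.05 calculation, the standardised effect is 0.499. A two-sided test needs 64 per group, or 64/0.955 = 67 for Mann-Whitney.
- If 64 came from a one-sided 0.05 calculation, the effect is 0.442. A two-sided test needs 81.3, so 82, or 81.3/0.955 = 85.2, so 86.

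All are below 100. With an assumed 90 evaluable per arm and efficiency 0.955, power is 90% or 82% respectively.

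**The case against.** The strongest reply is that the document says the trial is meant to explore. On that reading nothing is confirmatory and the defect is one of labelling. That would be fair if the plan were consistent about it, but it also sizes outcomes to detect differences, keeps a significance rule for everything and has a title that claims improvement. If exploration is the intent, the plan still has to say so and drop the rule.

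Four points about size deserve weight.

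- The lower figure of 10% is not a floor. At correlation 0.9 the three-test figure is 8.4%, and at 0.99 it is 6.0%. The document gives no correlation.
- The two-sided figures count errors in either direction. A false result favouring Exparel has a chance of 7.3%, 6.3% and 4.9% for three tests at correlation 0, 0.5 and 0.8, and of 28%, 17% and 10% for 13 tests.
- The plan does not say that each time point is tested separately, and repeated scores on the same patient are unlikely to be independent. The 49% is therefore an extreme.
- Length of stay is the last of the four aims, and the stated purpose is pain control. Its case as primary rests on its being already sized and needing no time point, not on its being the closest match to the question.

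These points limit the magnitude and leave the choice of endpoint to the sponsor. None supplies the missing primary endpoint or removes the freedom to choose after the fact.

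**Conclusion.** The concern holds, and it must be fixed before any between-group comparison. The document names no primary endpoint, no primary time point and no multiplicity control, and its one significance rule covers every analysis. With no true effect, testing each sized outcome once at two-sided 0.05 gives a significant result in one direction or the other with probability 14% if the outcomes are independent, falling to 10% at a common correlation of 0.8. With 13 tests the range is 49% to 19%. These figures rest on the assumed correlations, two-sided testing and, for the second range, the assumed count. With one-sided 0.05 tests the ranges are 9–14% and 17–49%. The absence of a primary endpoint rests on no assumption. As written, a single p-value below 0.05 among these outcomes could not support a confirmatory claim.

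**What to change.** Name one primary endpoint and replace the blanket rule in the Analysis section. With length of stay as primary the text could read: 'The primary endpoint is hospital length of stay, tested at two-sided 0.05. All other outcomes and time points are secondary or exploratory, are reported as estimates with 95% confidence intervals, and support no confirmatory claim.' If the sponsor prefers NRS pain or WOMAC change as closer to the purpose, the text must name one day or visit and show that the sized difference applies there. Opioid use has no sizing inputs, so its power cannot be checked as the plan stands.

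Two alternatives are open:

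1. Apply Holm's procedure across length of stay, NRS at one named day and WOMAC change at one named visit.
2. If the trial is only exploratory, label all outcomes so and drop the significance rule.

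**Cost.** Fewer results can be called significant. Length of stay as sole primary is a wording change and, on the assumptions in the working, needs no more patients. Holm costs power for length of stay, as follows (simulated; 80% power assumed in the plan's sizing; ranges cover correlation 0 to 0.5):

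| Assumed setting | All three planned effects hold | Only length of stay has an effect |
|---|---|---|
| Two-sided sizing, 100 per arm | 93–94% | 87% |
| One-sided sizing, 100 per arm | 86–87% | 76% |
| One-sided sizing, 100 per arm, efficiency 0.955 | 84–85% | 74% |
| One-sided sizing, 90 per arm, efficiency 0.955 | 80–81% | 68–69% |

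This loss favours a single primary endpoint. None of the options changes treatment, visits or the planned sample size.
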